9.2. Secondary Endpoint Analysis

The secondary endpoints that will be analyzed as part of this trial are as follows:

• Proportion of subjects with complete closure of the study ulcer at or before Week 12 and confirmed 2 weeks later as assessed by computerized planimetry.

Confidential Page 14 of 23

- Proportion of subjects with complete wound closure of the study ulcer at or before Week 12 and confirmed 2 weeks later as assessed by independent, blinded, assessment of photographs.
- The Time to complete wound closure, as assessed by the Investigator.
- The Time to complete wound closure, as assessed by computerized planimetry.
- For those wounds that have closed, the rate of wound closure for each group, as assessed by computerized planimetry.
- Medical resource utilization associated with management of DFU and related complications as determined by a comparison of estimated costs from the presumed billing codes which would have been used for each patient. The summary will be provided by an independent group, results will not be included in this analysis

Proportion of ulcers with complete wound closure during the treatment phase as assessed by planimetry will be compared using Logistic Regression with specified baseline covariates in the model.

Time to complete wound closure will be analyzed using the Log-rank test or Cox Proportional Regression Model. The Kaplan-Meier methods will be used to present the distribution of time to complete wound closure.

Summary statistics will be provided for the rate of wound closure for the two treatment groups.

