9.1 STATISTICAL ENDPOINTS

- Primary Efficacy Endpoint(s):

The primary endpoint of this study is the incidence of complete wound closure, as assessed by the Investigator at or before Week 12 of the Treatment Phase and confirmed closed 2 weeks later. Confirmed complete wound closure is defined as complete skin re-epithelialization that is without drainage or dressing requirements two weeks later.

A subject is considered to have a closed wound (i.e., a closure success) if the subject's treated wound closes between week 1 and 12 and is noted as closed on both follow-up visits.

A subject is considered to not have a closed wound (i.e., a closure failure) if they meet any of the following:

- the subject's treated wound does not close by week 12
- the subject's treated wound closes between week 1 and 12 and is noted as open on either or both of the follow-up visits.

A subject is considered to have an undetermined wound closure if the subject's treated wound closes between week 1 and 12 and the subject misses either or both of the follow-up visits. These subjects may become part of extended analyses.

- Secondary Efficacy Endpoint(s):
 1. Proportion of subjects with complete closure of the study ulcer at or before Week 12 as assessed by computerized planimetry.
 2. Proportion of subjects with complete wound closure of the study ulcer at or before Week 12 as assessed by independent, blinded, assessment of photographs.
 3. Time to complete wound closure, as assessed by the Investigator.
 4. Time to complete wound closure, as assessed by computerized planimetry.
 5. Rate of wound closure, as assessed by computerized planimetry.
 6. Medical resource utilization associated with treatment of DFU and related complications as determined by a comparison of estimated costs from the presumed billing codes which would have been used for each patient.

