8.3. Safety Population

The Safety population is defined as all subjects receiving the allocated treatment after randomization. This population will be used for the analysis of safety endpoints.

9. Description of Efficacy Endpoints and Analyses

The primary analysis of the primary efficacy endpoint will be performed using the ITT population. The sensitivity analysis of the primary endpoint will be performed using the PP population. All secondary efficacy endpoints will be performed using the ITT population. Safety analysis will be based on the safety population.

In efficacy or exploratory analyses, covariate analyses will be conducted to assess the impact of various prognostic factors on closure and to demonstrate the robustness of the primary analysis. Prognostic factors (i.e., covariates) will be included if they are found to be contributing factors (i.e., the individual covariate p-value is less than 0.10). Potential prognostic factors to be considered include:

• Ulcer area

Duration of ulcer

Gender

• HbA1c

•Ulcer Location

Diabetes type

• Race

• Nicotine Use

Baseline BMI

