9.4. Ad hoc Analyses

The following ad hoc analyses were designed.

- Number of applications per patient analysis, all wounds, healed, and non-healed wounds by treatment
- % of ulcer size reduction at the last visit of the treatment visit, all wounds, healed, and non-healed by treatment
- For all wounds, and non-healed wounds, the rate of wound closure for each group, as assessed by computerized planimetry by treatment

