11.1.2. Standard calculations

The following calculations will be used:

Equation 1. Age of Ulcer

$$Age = int \left(\frac{(date\ of\ ulcer\ at\ baseline - date\ of\ birth + 1)}{365.25} \right)$$

Equation 2. Clinical Trial Duration for a Subject

For subjects completing the study:

2a) Duration (days) = Final Follow up visit date - Randomization Visit Date

If a subject has not finished treatment (e.g., withdrawals, loss-to-follow-up, etc.)

2b) $Duration_{Withdrawal}(days) = Date \ of \ Withdrawal - Randomization \ Date + 1$

Equation 3. Duration of Adverse Events

 $Duration_{AE} = Onset\ Date_{AE} - Randomization\ Date_{AE} + 1$

Equation 4. Time to Complete Wound Closure

4a) Days to Complete Wound Closure $_{Investigator-based} = (Date\ of\ Last\ Confirmation\ Visit_{EDC}) - (Randomization\ Date) + 1$

Important: This metric will only be calculated for subjects who achieve investigator-based complete wound closure.

EDC: Indicates closure as defined in the EDC system; the investigator-noted closure.

Confidential Page 20 of 23

4b) Days to Complete Wound Closure_{Planimetric} = (Date of Last of Two Successive Readings of $0cm^2_{TA}$) – (Randomization Date) + 1

Important. Planimetric wound closure will only be calculated for subjects who achieve planimetric-based complete wound closure during the Treatment Phase.

TA: Size from imaging vendor (Tissue Analytics, Inc.) database.

Equation 5. Rate of Wound Closure

Rate of Wound Closure (
$$^{\%}$$
 Area/ $_{Week}$) = $\frac{7 \times (Area_{baseline} - Area_{final})}{Area_{baseline} \times Duration}$

Equation 6. Costs Associated with Applied CPT or DRG Codes

- 6a) $CPT\ Total\ Cost_{Study-Wide} = \sum Estimated\ Cost_{All\ Cohorts}$
- 6b) $CPT\ Total\ Cost_{Cohort\ X} = \sum Estimated\ Cost_{Schort\ X}$
- 6c) CPT Average $Cost_{Study-Wide} = \frac{\sum Estimated Costs_{Study-Wide}}{n_{all costs}}$
- 6d) $CPT \ Average \ Cost_{Cohort \ X} = \frac{\sum Estimated \ Costs_{Cohort \ X}}{n_{cohort-based \ costs}}$

Estimated Costs are based on CPT-10 codes.

Equation 7. Costs Associated with Use of Product

- 7a) $Cost \ All \ Product_{Study-Wide} = \sum Costs \ Per \ Product_{All \ Cohorts}$
- 7b) $Cost \ All \ Product_{Cohort \ X} = \sum Costs \ Per \ Product_{Cohort \ X}$

Confidential Page 21 of 23

7c) Average Cost All Product_{Study-Wide} =
$$\frac{\sum Costs \ Per \ Product_{Study-Wide}}{n_{all \ costs}}$$

7d) Average Cost All Product_{Cohort X} =

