11.1.3. Other Variables

Discontinuations

The difference between treatments, both overall and for each primary reason, will be compared by using a 2-sided Fisher's exact test.

Confidential Page 22 of 23

Demographic and Baseline Characteristics

Comparisons between treatment groups of continuous variables will be made by using a one-way analysis of variance with treatment as a factor. For categorical variables, the Fisher's exact test will be used. All tests will be 2-sided and performed at the 0.05 level of significance.

Time-to-Event Data

Time-to-event endpoints including time-to-complete-wound-closure/healed will be evaluated using the Kaplan-Meier method. The log-rank test will be used to compare the distributions between two treatment groups.

Rate of Wound Closure, as Assessed by Computerized planimetry

Analysis of Covariance (ANCOVA) will be used to compare the rate of wound closure for the two treatment groups.

Safety Data

The primary safety endpoint for this study is any severe device-related complication where relationship to the device was assessed by the clinical event committee possible, probably, or definite. Fisher's exact test will be used to compare incidence rates of serious device-related complications as well as for any device-related complication, and for specific complications between the treatment group and the control group.

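### The secondary rate of wound closure is limited to closed wounds in some places and not in others; read as SAP 9.2 words it, the comparison conditions on outcome and can favour the worse arm

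*SAP*

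**What the plan says.** The documents do not agree on which wounds enter this endpoint.

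- **Closed wounds only.** SAP 9.2 lists "For those wounds that have closed, the rate of wound closure for each group, as assessed by computerized planimetry". The protocol synopsis (Table 1) carries the same restriction.
- **No restriction.** Protocol 9.1 lists "Rate of wound closure, as assessed by computerized planimetry", and Table 3 does the same.
- **ITT.** The opening text of SAP Section 9 states: "All secondary efficacy endpoints will be performed using the ITT population".
- **Descriptive analysis.** SAP 9.2: "Summary statistics will be provided for the rate of wound closure for the two treatment groups".
- **Test.** SAP 11.1.3: "Analysis of Covariance (ANCOVA) will be used to compare the rate of wound closure for the two treatment groups". It names no population and no covariate. SAP 10.1 sets tests at two-sided 0.05 unless otherwise specified.
- **Other populations.** SAP 9.4 adds, as an ad hoc item, "For all wounds, and non-healed wounds, the rate of wound closure for each group, as assessed by computerized planimetry by treatment".

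SAP 11.1.2 gives the formula (Equation 5): 7 × (baseline area − final area) / (baseline area × Duration). Duration is not defined for this use. Protocol 9.4.6 describes the secondary analyses as exploratory.

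**The concern.** Closure by Week 12 happens after randomization and is what the treatments are meant to bring about. If arms are compared only among wounds that closed, the compared subsets were formed by the outcome and randomization no longer protects the comparison. An arm that also closes hard, slow wounds brings those slow closures into its average. An arm that leaves them open omits them. The better arm can then show the lower rate, possibly with a nominal p-value attached.

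The formula adds to this. In closed wounds it carries no information about area, only about time, so it largely repeats the time-to-closure endpoint in a selected subset.

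**Working it through.** The documents give no design figure for this endpoint, so there is nothing of the plan's own to reproduce. Their one precision figure (13.5%) concerns the closure proportion. All closure times below are assumptions, because the documents give none by arm.

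**Step 1. Equation 5 in a closed wound.** Put final area = 0. Baseline area cancels, leaving 7/Duration as a fraction per week with Duration in days, or 700/Duration in % per week. With time in weeks this is 100/weeks. It assumes that a wound counted as closed reads 0 cm² on planimetry.

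**Step 2. Hand example, Duration taken to closure.**
- Arm S closes 40% of wounds, all at 6 weeks: 100/6 = 16.7 %/week.
- Arm T closes 40% at 5 weeks (20.0 %/week) and another 40% at 11 weeks (9.09 %/week): (0.4 × 20.0 + 0.4 × 9.09)/0.8 = 14.5 %/week.

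Arm T closes twice as many wounds, and its early closers are faster, yet its closed-only rate is lower.

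**Step 3. Same example with Duration run to the final follow-up visit, as in Equation 2a (two weeks later).** Arm S: 100/8 = 12.5. Arm T: (100/7 + 100/13)/2 = 11.0. The figures change; the direction does not.

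**Step 4. Same example on all wounds, Duration to closure or 12 weeks.**

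| Assumed rate in open wounds | Arm T | Arm S |
|---|---|---|
| 0 | 0.8 × 14.5 = 11.6 | 0.4 × 16.7 = 6.7 |
| 100/12 = 8.3 %/week (almost full shrinkage) | 11.6 + 0.2 × 8.3 = 13.3 | 6.7 + 0.6 × 8.3 = 11.7 |

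The order is restored at both ends of the range, given equal shrinkage of open wounds in both arms.

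**Step 5. How often reversal occurs.** Simulation with 38 per arm and a two-sample t-test in place of ANCOVA; 10,000 replicates for the main scenario, 4,000 for the others.

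Main scenario: 40% of each arm closes at weeks 2–6. The better arm also closes 35% at weeks 8–12, the worse arm 5% (total closure 75% v 45%). Open wounds shrink by 0 to 80% over 12 weeks.
- Closed-only mean rate: 20.3 (better arm) v 26.9 (worse arm) %/week. It favours the worse arm in 95.5% of trials, with p<0.05 in 38.5%. With 30 per arm these are 93% and 31%.
- All wounds: 16.0 v 13.9 %/week. The better arm is favoured in 74%.

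Varying the better arm's excess of late closures:

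| Excess (percentage points) | Closed-only rate favours worse arm |
|---|---|
| 5 | 65% |
| 10 | 76% |
| 20 | 90% |
| 40 | 98% |

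If the better arm instead raises a constant weekly closure chance, the worse arm is favoured in 28% of trials (0.12 v 0.06) or 37% (0.10 v 0.07).

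**Step 6. The all-wounds rate has its own weakness.** SAP 9.5 carries forward the last planimetric value for discontinued subjects. If Duration stops at dropout, a subject who leaves at week 1 with 20% shrinkage scores 20 %/week, above a wound that closes at week 6 (16.7). With Duration fixed at 12 weeks the same subject scores 20/12 = 1.7 %/week.

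**The case against.** The strongest reply is that the documents do not commit to a closed-only test. SAP 9.2 promises only summary statistics for the rate, the ANCOVA sentence in SAP 11.1.3 does not mention closed wounds, SAP Section 9 points to the ITT population, and SAP 9.4 already plans the rate in all wounds. This stands. A reader might infer that the ANCOVA is specified on the closed subset; the text does not say so. It leaves the population open, and the only SAP definition of this secondary endpoint is the restricted one. The ITT sentence does not settle it, because it can be read as naming the parent set within which SAP 9.2 then filters.

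A reader might also infer that the closed-only rate must mislead. It need not: under uniformly faster closure it pointed the wrong way in 28% to 37% of simulated trials. The hand example is also far from the plan's own assumption of 90% closure with no difference between arms.

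Nor is the all-wounds rate simply unbiased. It removes the selection on closure but depends on the dropout rule and on Duration, and the ITT set in SAP 8.1 leaves out randomized subjects who received no application.

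Finally, the consequence is limited. The primary endpoint is the closure proportion, and log-rank or Cox analysis of time to closure is planned, so a reversed rate would be read beside those results.

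**Conclusion.** The point holds in two parts. First, the population for this endpoint is inconsistent: the synopsis and SAP 9.2 restrict it, protocol Table 3 and Section 9.1 do not, and SAP Section 9 says ITT. Second, if the SAP 9.2 definition governs the comparison, it conditions on a post-randomization outcome and can rank the arms the wrong way.

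The size depends on the healing pattern. Reversal is likely when the better arm's gain comes mainly from late closures (65% to 98% of simulated trials for an excess of 5 to 40 points) and less likely when closure is uniformly faster. These figures rest on assumed closure times, on closed wounds reading 0 cm², and on a t-test standing in for ANCOVA.

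Impact is moderate, because the endpoint is secondary and exploratory and the SAP states that the trial is not adequately powered for hypothesis testing.

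**What to change.** 1. Make the rate in all wounds of the ITT population, already listed in SAP 9.4, the secondary analysis and the one tested by ANCOVA, with baseline ulcer area as covariate. This agrees with protocol Table 3, protocol 9.1 and SAP Section 9.
2. Define Duration in Equation 5: randomization to closure for closed wounds, and the full 12-week treatment period for wounds not closed. Dropouts before closure belong to the second group, with the last planimetric value carried forward, so that leaving early cannot inflate the rate.
3. State whether closed means by investigator or by planimetry, and which arm pairs are meant by two treatment groups in a three-arm trial.
4. Report closed-only and non-healed rates descriptively, without a test.
5. Record the change and its reason in SAP Section 12.

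No new data are needed. The costs are a departure from the synopsis and SAP 9.2 wording, and the promotion of an analysis now listed as ad hoc. Because data review is not blinded and SAP Section 12 shows that some outcome data had already been evaluated, that promotion carries a selection risk of its own and should be disclosed. The all-wounds result will still depend on the dropout rule.

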9.3. Exploratory Endpoint Analysis

Exploratory analyses will be performed to examine wound closure status at Week 4 of Treatment and wound closure status at the 2-week follow-up visit

Proportion of subjects with confirmed complete wound closure of the study ulcer at week 4 Treatment Phase, and at the 2-week follow-up visit as assessed by computerized planimetry for each of the treatment groups will be summarized. A point estimate will be presented along with the exact 95% confidence interval based on the binomial distribution.

Exploratory analysis to identify prognostic factors for predicting complete wound closure may be performed. Prognostic factors (i.e., covariates) will be included if they are found to be contributing factors (i.e., the individual covariate p-value is less than 0.10). Potential prognostic factors to be considered include:

• Ulcer area

• Duration of ulcer

Confidential Page 15 of 23

Gender

- HbA1c
- •Ulcer Location
- Diabetes type

Race

- Nicotine Use
- Baseline BMI

9.4. Ad hoc Analyses

The following ad hoc analyses were designed.

- Number of applications per patient analysis, all wounds, healed, and non-healed wounds by treatment
- % of ulcer size reduction at the last visit of the treatment visit, all wounds, healed, and non-healed by treatment
- For all wounds, and non-healed wounds, the rate of wound closure for each group, as assessed by computerized planimetry by treatment

9.5. Missing Data

For primary efficacy evaluation of data points, the last available observation (LOCF) will be used. In the analyses of using the planimetry data, the last available planimetric value will be used for a discontinued subject. All subjects discontinued during the treatment period and before 100% wound closure during the treatment phase of the study will not be replaced and will be considered treatment failures for evaluating the primary and secondary endpoints.

10. Description of Other Variables and Analyses

10.1. General Statistical Considerations

All study data collected in the eCRF will be presented in subject data listings. Statistical analyses will be performed using SAS® for Windows, version 9.4 or later. Descriptive statistics (e.g., n, mean, standard deviation, median, etc.) will be calculated by treatment group for continuous variables. Frequencies and percentages will be presented by treatment group for categorical variables.

Unless otherwise specified, all testing will be performed using two-sided test at the 0.05 level of significance.

Confidential Page 16 of 23

10.2. Study Subjects

10.2.1. Subject Disposition

The disposition of all subjects who sign an ICF will be provided. The numbers of subjects screened, randomized, completed, and discontinued during the study, as well as the reasons for all post-randomization discontinuations will be summarized by treatment group, for all sites combined and each site separately. Disposition and reason for study discontinuation will also be provided as a by-subject listing.

10.2.2. Discontinuations and Protocol Deviation

Protocol deviations will be identified and listed by study sites based on the definitions and constraints set forth in section 10.1.9 of the protocol.

10.2.3. Demographic and Baseline Characteristics

Demographic data including but not limited to age, race, gender, ethnicity, nicotine use and other baseline characteristics, but not limited to medical and surgical history will be tabulated by treatment and overall. Summarized demographic data will include mean, standard deviation, median, minimum and maximum; as well as analogous summary statistics for presenting diagnosis and other relevant patient characteristic factors.

Physical examination (including vitals) will be performed and data will be summarized using descriptive statistics.

10.3. Concomitant Medications and Medical History

Concomitant Medications and Medical History data will be listed for each subject.

10.4. Ulcer Assessment

Data for below questions will summarized by visit using descriptive statistics

- Ulcer Infection Assessment
- Location of Study Ulcer
- Extent of Ulceration
- Ulcer Infection Assessment
- Investigator Assessment of Wound Closure
- Ulcer Exudate Assessment

Confidential Page 17 of 23

Compliance Assessment

10.5. Ulcer Treatment

Data for below questions will be summarized using descriptive statistics by visit.

- Investigational Product Information
- Investigational Product Outer Dressings
- AMNIOEXCEL® Plus Re-application
- Apligraf[®] Re-application
- Sharp Debridement
- Ulcer Photography
- Standard of Care Treatment,
- Dressing Supplies
- Off-loading Information

10.6. Safety Analysis

Safety will be assessed through reports of adverse events and serious adverse events. Adverse Events related to the device, study ulcer and/or study procedures and all Serious Adverse Events will be recorded.

All safety parameters will be summarized descriptively by treatment. No inferential statistics are planned.

10.7. Adverse Events

Adverse events will be coded using the MedDRA Medical Dictionary. Treatment Emergent AE's (TEAE) are defined as events with an onset on or after the first randomized treatment. TEAEs will be summarized by treatment group, System Organ Class, and preferred term. The following TEAE summaries will be provided:

- TEAEs by severity grade
- TEAEs by relationship to study treatment.

In addition, separate summaries of serious adverse events, and adverse events resulting in discontinuation of study treatment will be presented.

The safety population will be used for the safety analyses. Summary will be provided by subject and by adverse events. Subjects will be counted only once for subject-based analysis.

Confidential Page 18 of 23

If the same event changes in severity for a subject, the worst severity will be reported. Subjects could be counted more than once for AE-based analysis, all AEs will be reported for AE-based analysis.

An adverse event is considered to be treatment emergent if (1) it was not present when the active phase of the study began, and it is not a chronic condition that is part of the subject's medical history; or (2) it is present at the start of the study or as part of the subject's medical history, but the severity or frequency increased during the active phase. The active phase of the study begins on the day of the first dose of test article and the last dose of test article.

Treatment-emergent adverse events (TEAE) will be summarized for each treatment group by body system and preferred term. The severity of all adverse events will be determined by the investigator's judgment and classified as mild, moderate or severe.

Treatment groups will be compared with respect to the incidence of adverse events (all and TEAEs) and the proportion of subjects withdrawing from the study for adverse events by reason of withdrawal. Comparisons will be made overall, by body system and by preferred term and will be further categorized by severity and by study drug relationship.

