6.1.2.3 RECOMMENDED INSTRUCTIONS FOR USE OF APLIGRAF²⁶

More information about application of the product can be found on manufacturer's website: [http://www.apligraf.com/professional/what is apligraf/how is it applied/index.html](http://www.apligraf.com/professional/what_is_apligraf/how_is_it_applied/index.html)

1. Wound Bed Preparation:
 - When applying Apligraf there should be no signs of infection (see Section 7.1 for subjects who become infected during the course of the study).
 - The wound bed should be prepared with appropriate method of debridement
2. Placement of the Apligraf®

- If desired, fenestrate Apligraf® with a knife blade or mesh (1.5-1 ratio). Apply Apligraf to wound and affix with method of preference i.e., Steri-Strips™, wound glue at periphery, or sutures
- 3. Primary Dressing
 - Cover Apligraf® with primary non-adherent dressing
- 4. Secondary Dressing
 - Apply appropriate dressing determined by wound type. A non-cytotoxic antimicrobial may also be applied at this time.
 - Provide Offloading for DFU
 - Keep dressing dry until first follow-up appointment.
- 5. First Follow-up
 - At Week 1 follow up, remove secondary dressing only for wound inspection and evaluation. Primary dressing (non-adherent) should be left undisturbed to facilitate integration of Apligraf®.
- 6. Application of Secondary Dressing
 - Reapply appropriate secondary dressings
- 7. Subsequent Follow-ups
 - On second follow up (14 days, Week 2), remove secondary and primary dressing for wound inspection and evaluation. Do not disturb or debride the wound bed. Perform light normal saline wash
- 8. Application of Primary and Secondary Dressings
 - Apply new primary (shown) and secondary dressings
 - On subsequent weekly follow-ups, continue to change primary and secondary dressings to monitor wound healing.
 - Apligraf may be reapplied if needed until wound healing is complete, as shown.

Additionally, the site should refer to Apligraf's Instructions for Use documents that are supplied with the product and/or consult an Apligraf representative for appropriate training.

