8.3 ADVERSE EVENTS AND SERIOUS ADVERSE EVENTS

8.3.1 DEFINITION OF ADVERSE EVENT (AE)

For the purposes of this research protocol, an **adverse event** means any untoward medical occurrence or adverse reaction (AR) associated with the use of an intervention in humans, that is considered possibly, probably, or definitely-related to the investigational product or study procedure. All events starting or worsening after the first randomized treatment through study exit will also be collected.

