8.3.2 DEFINITION OF INVESTIGATIONAL PRODUCT

Investigational Product is defined as either the AMNIOEXCEL Plus or Apligraf allograft.

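### SAP 10.7 defines treatment-emergent events twice; the second definition can leave out worsening after the last application and does not fit the SOC arm as written

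*SAP*

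**What the plan says.** SAP 10.7 opens with a simple rule: "Treatment Emergent AE's (TEAE) are defined as events with an onset on or after the first randomized treatment". It states no end date and does not mention worsening.

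Later in the same section a second rule appears, with two limbs:

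- Limb (1), new events: "it was not present when the active phase of the study began, and it is not a chronic condition" belonging to the medical history.
- Limb (2), conditions present at the start or in the history: "but the severity or frequency increased during the active phase".

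The phase on which both limbs depend is then described: "The active phase of the study begins on the day of the first dose of test article and the last dose of test article". The sentence gives no end point in so many words, and neither document defines *test article*.

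Protocol 8.3.1 sets what is collected: "All events starting or worsening after the first randomized treatment through study exit will also be collected". Protocol 8.3.2 is the nearest thing to a definition of the product: "Investigational Product is defined as either the AMNIOEXCEL Plus or Apligraf allograft". SAP 8.3 puts everyone who receives the allocated treatment in the safety population, which includes SOC subjects.

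**The concern.** The two rules classify some events differently, and neither matches the window in Protocol 8.3.1. A programmer has to choose one, or merge them, without guidance.

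Worsening matters in this trial because every subject enters with an open ulcer. Protocol 8.3.7 records deterioration of a pre-existing condition as an AE, and Protocol 8.3.6.3 lists ulcer enlargement, tunneling and undermining among the anticipated adverse events. If worsening counts only up to the last application, the time at risk for that type of event depends on when the wound closed. A TEAE table by arm would then mix safety with the efficacy result.

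The second rule also cannot be applied to SOC without deciding what *test article* means. SAP 6 states that the trial is open label with no analytical blinding. A choice left open could therefore be made with results in view.

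**Working it through.** The documents give no figure for the TEAE window, so there is none to reproduce. The check compares the definitions and then applies the visit schedule.

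**Step 1. Definitions side by side (graft arms).** This assumes that the active phase ends at the last application, the likeliest repair of the sentence.

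| Event | First definition | Second definition | Protocol 8.3.1 |
|---|---|---|---|
| New, before last application | counts | counts | collected |
| New, after last application | counts; no end date | counts; limb (1) has no end | collected |
| Pre-existing, worsens before last application | not stated | counts | collected |
| Pre-existing, worsens after last application | not stated | does not count | collected |

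Only the last row loses events under the second definition.

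**Step 2. Time affected.** Inputs, at nominal visit days and ignoring the ±3-day windows:

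- Both grafts are applied weekly while the ulcer is open, up to Week 11 (Protocol 6.1.1.1).
- A closed wound is followed for two more weeks, and an ulcer not closed by Week 12 has no further visits (Protocol 7.1).
- A subject whose wound is open at the first follow-up visit exits then (Protocol 7.2).

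For closure first seen at Week k, the last application is on day 7(k−1) and exit is on day 7(k+2). The share of observed time after the last application is 21/[7(k+2)] = 3/(k+2).

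| Course | Last application | Exit | Share after last application |
|---|---|---|---|
| Closed at Week 4 | day 21 | day 42 | 21/42 = 50.0% |
| Closed at Week 6 | day 35 | day 56 | 21/56 = 37.5% |
| Closed at Week 8 | day 49 | day 70 | 21/70 = 30.0% |
| Closed at Week 12 | day 77 | day 98 | 21/98 = 21.4% |
| Closed at Week 12, open at first follow-up visit | day 77 | day 91 | 14/91 = 15.4% |
| Still open at Week 12 | day 77 | day 84 | 7/84 = 8.3% |

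These are shares of time in which a worsening event would not qualify. They are not shares of events lost.

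**Step 3. Apligraf schedule.** Protocol 6.1.1.1 has Apligraf applied weekly. Protocol 6.1.2.3 says "Apligraf may be reapplied if needed until wound healing is complete, as shown". If the second text governs, the last application may come earlier. For an ulcer still open at Week 12, an assumed last application at Week 8, Week 4 or Day 0 gives 28/84 = 33%, 56/84 = 67% or 84/84 = 100%. The two passages must be reconciled; this point does not depend on which one is kept.

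**Step 4. SOC.** If *test article* means the allografts of Protocol 8.3.2, a SOC subject has no first or last dose. The active phase then has neither start nor end, and both limbs of the second definition fail. The first definition still works for SOC.

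**Step 5. After the fix.** With a window from first randomized treatment through study exit, no on-study time after that treatment is excluded in any arm.

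**The case against.** A reader might infer that all events in Weeks 12 to 14 drop out, including infections or immune reactions after the final graft. The text does not support this. Limb (1) asks only whether the event was present when the phase began, and the first definition is open-ended, so new events after the last graft count under either. Nor is the affected period Weeks 12 to 14 in general: for closure at Week 4 it is days 21 to 42.

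A reader might also infer that SOC has no TEAE window at all. That is true only under the second definition, and only if *test article* means the allografts.

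A third inference is that the excluded share differs between the graft arms. The plan assumes equal closure (SAP 5), and with weekly grafting in both arms the shares are then the same. They differ only if closure differs or Apligraf is reapplied less often than weekly. Neither is established.

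Two further objections have some force:

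- Protocol 8.3.7 records deterioration as an AE. If the onset date entered is the date of deterioration, the first definition would capture it. That is a reasonable convention, but the SAP does not state it, and it does not remove the conflict with limb (2).
- Events are not lost from reporting. SAP 10.7 compares all AEs as well as TEAEs, with separate summaries of serious events and of discontinuations. The defect is therefore misclassification. The all-AE comparison is not a full substitute, because AE recording starts in screening and so includes events before randomized treatment.

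Finally, the end of the active phase at the last dose is an interpretation of a broken sentence. It is the natural one, but the SAP does not say it outright.

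**Conclusion.** The point holds in a limited form. SAP 10.7 contains two TEAE definitions that disagree, and neither matches Protocol 8.3.1. If the active phase ends at the last application, worsening of a pre-existing condition, including the study ulcer, is not treatment-emergent under the second definition for the last 8% of observed time in a non-closer, 21% for closure at Week 12 and 50% for closure at Week 4. The exclusion therefore depends on the efficacy outcome. The second definition cannot be applied to SOC if *test article* means the allografts.

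The figures assume weekly grafting with no application withheld, nominal visit days and completion of the scheduled visits. How many events would be reclassified cannot be derived from the documents. New-onset events after the last graft are unaffected, and no imbalance between arms has been shown. This should be corrected before the safety tables are programmed, but it does not put the safety data themselves at risk.

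**What to change.** Delete the active-phase sentence and the second definition that relies on it. Use one definition in all three arms: a TEAE is an event that starts, or worsens in severity or frequency, on or after the first randomized treatment (graft or SOC) and up to study exit. State that the onset date of a worsening event is the date of deterioration, so that Protocol 8.3.7 and the SAP agree. Remove *test article* or define it.

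Optionally, add TEAEs per subject-week as a descriptive column beside the percentages. Observed time is 6 weeks for closure at Week 4, 12 weeks for a non-closer and 14 weeks for closure at Week 12, so percentages alone compare unequal follow-up. This follows from the design and is not needed to repair the definition.

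The cost is SAP wording and minor programming. No new data are needed. TEAE counts may rise slightly.
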